### 5.2.1 Safety Lead-In

The study will initiate with a Safety Lead-In of 6 subjects. The first dose of study agent (Avelumab) will be administered after all procedures / assessments have been completed as detailed on the **Schedule of Events (Attachment 1)**. Avelumab will initially be administered at 10 mg/kg (IV) every 2 weeks (Dose Level 0, see **Table 1** below), which is the RP2D established for monotherapy administration (see section 1.4, Dose Rationale).

Beginning 7 days after the first dose of Avelumab (i.e. Day 8), all subjects will be administered HFRT to a total of 25 Gy, given in 5 fractions of 5 Gy on consecutive days (i.e., Day 8 to Day 12). Avelumab will continue to be given once every 2 weeks after the first Avelumab dose.

Once the initial 6 subjects are enrolled in the Safety Lead-In, enrollment will stop and subjects will be observed for 28 days for dose-limiting toxicities (DLTs, see **DLT definitions, Section 5.2.1.2**). At the end of the DLT period of 28 days, a **Safety Monitoring Team** consisting of the overall PI ([name], PhD), the Deputy Director of the Perlmutter Cancer Center who is not an investigator on the study, and the study biostatistician will review the safety data at a Safety Lead-In Dose Review meeting. This meeting will be led by the overall PI and at a minimum will be attended by the Safety Monitoring Team, the NYULMC Data Safety Monitoring Committee (DSMC), and a designated representative from each study site; other individuals, including sub-investigators, may be included. Continuation of enrollment will occur once all of the initial 6 subjects have completed the Day 28 safety assessments and the final dosing decision is made by the Safety Monitoring Team. However, screening for the next dose cohort may begin prior to confirmation that the current dose is safe.

The Safety Lead-In incorporates a de-escalation of Avelumab dosing if unexpected DLT is observed in the first 6 subjects. The Safety Monitoring Team and NYULMC DSMC will review the safety data at the end of the DLT period for the first 6 subjects and determine whether the study should proceed to phase II at Dose Level 0 or enter the dose de-escalation phase, which will follow a 3+3 phase I design. In the dose de-escalation phase, subjects will be enrolled and observed in groups of 3 for DLTs for an evaluation period of 28 days (see Dose De-Escalation Rules, **Section 5.2.1.1**, and **Study Schema, Section 3.1.1**). After 3 subjects are enrolled in each cohort, enrollment will stop and subjects will be observed for 28 days for DLTs. At the end of the DLT period, the Safety Monitoring Team and NYULMC DSMC will review the safety data at a Safety Lead-In Dose Review meeting that will include at least a representative from each site; sub-investigators may be included. Continuation of enrollment will occur once all 3 of the subjects have completed the Day 28 safety assessments and the final dosing decision is made by the Safety Monitoring Team. However, screening for the next dose cohort may begin prior to confirmation that the current dose is safe.

DLT will be determined by toxicities related to Avelumab during or beginning over the first 28 days of treatment as defined below in **Section 5.2.1.2 (Definition of DLT in for the Safety Lead-In)**. Subjects who experience DLT will be discontinued from study therapy and will enter the post-study follow-up phase of the study. Adverse events that meet DLT criteria but occur outside the DLT window will be classified as unacceptable AEs and study treatment will be discontinued.

Subjects are evaluable for DLTs if they have received at least one dose of Avelumab, have completed HFRT per protocol and have completed safety assessments over the entire DLT evaluation period (days 1 through 28). Any subject who discontinues treatment or withdraws from the study prior to completing the DLT evaluation period for any reason other than the occurrence of a protocol-defined DLT or other AE leading to study treatment discontinuation will be replaced (see also **Section 7.3.1**). Each replacement patient will be assigned a unique patient number, and will be treated at the same dose level as the replaced, prematurely withdrawn patient. Any patient who discontinues after the DLT observation period will not be replaced.

CONFIDENTIAL

Subjects who do not experience a DLT during the DLT period (28 days) and remain on study after the DLT period will continue Avelumab administration every 2 weeks for up to 2 years or until the subject discontinues study therapy as per Subject Withdrawal guidelines (**Section 4.5**). Subjects in the Safety Lead-In who are discontinued from study therapy may be considered for treatment resumption after resolution or stabilization of the condition if resuming treatment is thought to be in the best interest of the patient, however treatment may resume only after discussion with the Safety Monitoring Team, NYULMC DSMC and overall PI (see **Section 5.2.6.2**). Otherwise, all subjects who discontinue study therapy will enter the post-study follow-up phase of the study as per **Section 4.4.2**.

#### 5.2.1.1 Dose De-Escalation Rules

- If at **Dose Level 0**,  $\leq 1$  of the first 6 subjects develop DLT, the study will continue to phase II at Dose Level 0, which will be considered the **RP2D**.
- If at **Dose Level 0**,  $>1$  of the first 6 subjects develop DLT, cohort enrollment will be stopped immediately, and re-started from the beginning with 3+3 patients enrolled at Dose Level -1.
- If at **Dose Level -1**,  $\leq 1$  of the first 3 subjects develop DLT, 3 more subjects will be enrolled to Dose Level -1.
- If at **Dose Level -1**,  $\leq 1$  of the first 6 subjects develop DLT, the study will continue to phase II at Dose Level -1, which will be considered the **RP2D**.
- If at **Dose Level -1**,  $>1$  of the first 3 subjects develop DLT, cohort enrollment will be stopped immediately, and re-started from the beginning with 3+3 patients enrolled at Dose Level -2.
- If at **Dose Level -1**,  $>1$  of 6 subjects develop DLT, cohort enrollment will be stopped immediately, and re-started from the beginning with 3+3 patients enrolled at Dose Level -2.
- If at **Dose Level -2**,  $\leq 1$  of the first 3 subjects develop DLT, 3 more subjects will be enrolled to Dose Level -2.
- If at **Dose Level -2**,  $>1$  of the first 3 subjects develop DLT, the Safety Lead-In will be discontinued. In this case, the phase II portion of this study will not be conducted.
- If at **Dose Level -2**,  $\leq 1$  of the first 6 subjects develop DLT, the study will continue to phase II at Dose Level -2, which will be considered the **RP2D**.
- If at **Dose level -2**,  $>1$  of the first 6 subjects develops DLT, the Safety Lead-In will be discontinued. In this case, the phase II portion of this study will not be conducted.

**Table 1: Dose levels and doses to be evaluated in Safety Lead-In and for dose reductions**

Dose Level	Avelumab Dose (mg/kg)
Zero (0)	10 mg/kg
Minus one (-1)	3 mg/kg
Minus two (-2)	1 mg/kg

#### 5.2.1.2 Definition of Dose-Limiting Toxicity (DLT) for the Safety Lead-In

A DLT is defined as any grade  $\geq 3$  adverse event (AE) that is at least possibly, probably or definitely related to Avelumab or HFRT during the DLT period with the exceptions noted below.

CONFIDENTIAL

This material is the property of the NYU School of Medicine and Langone Medical Center. Do not disclose or use except as authorized in writing by the study sponsor

For guidance on assessing the relationship of AEs to Avelumab, HFRT, or study procedures, see **Attachment 5**. The sponsor may request information to justify the causality assessment of DLTs, as needed.

The DLT period is considered the first 28 days of study therapy, and will include labs and other evaluations taken at C1D28 (end of the first 28 days). The frequency, time to onset, and severity of toxicities, as well as the success of standard medical management and dosing interruptions/delays, will be analyzed to determine if a given toxicity should be considered a DLT for dose decision purposes. The final decision of whether or not the AE meets the DLT definition will be based on a careful review of all relevant data by the Safety Monitoring Team. The investigator may also be consulted.

In addition to the above, the following DLT exceptions will apply:

A DLT will be defined as any of the following:

- Grade  $\geq 2$  uveitis (considered as a potential **immune-related adverse event [irAEs** – see definition in **Section 5.2.3.3]**)
- Any Grade 4 AE **except** for single laboratory values out of normal range that are unlikely related to study treatment as described below in the DLT exceptions.

The following exceptions will **NOT** be classified as DLT:

- Grade 4 single laboratory values out of normal range that are unlikely related to study treatment as assessed by the Investigator, do not have any clinical correlate, and resolve within 7 days with adequate medical management
- Grade 3 **immune-related adverse events (irAEs** – see definition in **Section 5.2.3.3** and **Attachment 4**) other than uveitis that downgrade to Grade  $\leq 2$  within 14 days after onset of the event with maximal supportive care, including systemic corticosteroids.
- Grade 3 asymptomatic endocrinopathy, managed with or without systemic corticosteroid therapy and/or hormone replacement therapy.
- Grade  $\leq 3$  symptoms attributable to brain edema, per details in the **Rules for Brain Edema** below.
- Any pre-existing lab abnormality that deteriorates to Grade 3 or 4 that is considered unlikely related to study treatment as assessed by the Investigator, do not have any clinical correlate, and resolves within 7 days with adequate medical management.
- Transient ( $\leq 6$  hours) Grade 3 flu-like symptoms or fever, which is controlled with medical management
- Transient ( $\leq 24$  hours) Grade 3 fatigue, local reactions, headache, nausea, emesis that resolves to Grade  $\leq 1$ .
- Change in KPS to  $< 60$  that resolves to  $\geq 60$  within 14 days

While rules for adjudicating DLTs are specified above, an AE of Grade  $< 3$  (except if listed as exempt above), may also be defined as a DLT after a consultation with the overall study Principal Investigator, based on the emerging safety profile of Avelumab. In the absence of clinical abnormality, repeat laboratory testing will be conducted to confirm significant laboratory findings prior to designation as a DLT.

CONFIDENTIAL

irAEs are defined as AEs of immune nature (i.e., inflammatory) in the absence of a clear alternative etiology (see **Section 5.2.3.3** and **Attachment 4** for Definitions and guidelines for management of irAEs).

Note: See **Section 8.1, Adverse Event Definitions**, for expected AEs related to Avelumab.

Note, any AE that meets DLT criteria will be considered an AESI and must be reported to the study sponsor (overall PI) within 24 hours of awareness of the event per **Section 8.3.1**. The study sponsor or designee will then notify the NYULMC PCC DSMC and IRB within 24 hours of awareness of the event.

**Rules for Brain Edema**: Development of edema in the brain is common following fractionated brain radiation therapy and may be asymptomatic (solely a radiographic finding) or associated with mild, moderate or severe symptoms. Therefore, brain edema will be considered an **expected** event related to study therapy (HFRT) and will **not** be considered a DLT unless brain edema meets CTCAE 4.03 criteria for "**Edema cerebral**" which only has a severity of Grade 4.

Note: **Grade 4 "Edema cerebral"** should only be used if the event meets CTCAE v4.03 criteria (i.e., Life-threatening consequences; urgent intervention indicated). Grade 4 Edema cerebral is considered a DLT and is defined by any of the following criteria:

- Any neurosurgical procedure is required to manage brain edema
- Requires an osmotic diuretic for management of symptomatic brain edema
- Requires >8 mg per day of dexamethasone or bioequivalent for more than 7 consecutive days to manage symptoms of brain edema
- Brain edema is deemed life-threatening per judgment of the treating investigator

Subjects who experience Edema cerebral Grade 4 will discontinue Avelumab immediately and will enter the post-study follow-up phase of the study. The overall PI may request additional information on events classified as Grade 4 cerebral edema.

For study purposes, the AEs deemed attributable to brain edema that do not meet Edema cerebral Grade 4 per CTCAE v4.03 should be described by the symptom (e.g. headache, nausea, focal neurological deficit) and graded for severity accordingly. If appropriate, the investigator should use the term "**Central nervous system necrosis**" per CTCAE 4.03 criteria if the investigator deems the radiographic findings are consistent with central nervous system radiation necrosis without symptomatic Grade 4 severity. Grade  $\leq 3$  AEs that are attributable brain edema or central nervous system necrosis will **not** be classified as DLT if:

- The grade 3 AE downgrades to Grade  $\leq 2$  within 7 days, or to Grade  $\leq 1$  or baseline within 14 days after onset of the event with maximal supportive care, including bevacizumab (see bevacizumab guidelines below) and/or systemic corticosteroid administration (no more than 7 consecutive days of dexamethasone dosed at >8 mg per day or bioequivalent).
- The grade 2 AE improves to grade  $\leq 1$  or baseline within 14 days after onset of the event with maximal supportive care, including bevacizumab and/or systemic corticosteroid administration (no more than 7 consecutive days of dexamethasone dosed at >8 mg per day or bioequivalent).

Note: For subjects who are suspected to have study treatment-related symptomatic intracranial or brain edema at any time during the study, Avelumab dosing should be

CONFIDENTIAL

immediately interrupted. **VEGF inhibition is preferred over corticosteroids** for management of suspected intracranial or brain edema, radiation necrosis, or intracranial hypertension, due to the risk that corticosteroids may suppress immune response against the tumor. Bevacizumab was granted accelerated approval by the US FDA for use as monotherapy in progressive GBM based on two historically-controlled, single-arm or non-comparative phase II trials however the addition of bevacizumab to standard of care in newly diagnosed GBM or to lomustine in recurrent GBM failed to show a benefit in overall survival in multi-institutional, randomized phase III trials. Therefore, the addition of bevacizumab should not alter the survival outcomes of the study regimen. In addition, bevacizumab has been reported to be safe in combination with anti-PD-1/PD-L1 pathway inhibitors and re-irradiation to 30 Gy in a phase I trial of recurrent GBM patients, and the combination of bevacizumab with anti-PD-1/PD-L1 pathway inhibitors is being investigated in a number of clinical trials, including for gliomas.

The VEGF inhibition strategy will be **bevacizumab (at a maximal dose of 10 mg/kg IV) every 2 weeks, for a minimum of 2 doses**. If VEGF inhibition does not resolve the symptoms to grade  $\leq 1$  or baseline, the investigator may institute systemic corticosteroids, in addition to or as a replacement for bevacizumab, at the lowest dose that is appropriate for symptom management.

If the symptoms improve to grade  $\leq 1$  or baseline by 2 weeks after the last dose of Avelumab, the subject may stop bevacizumab and continue Avelumab on study. If symptoms do not improve to grade  $\leq 1$  or baseline by 2 weeks after the last dose of Avelumab, the subject must permanently discontinue study treatment. If a subject requires a neurosurgical procedure or mannitol to manage grade  $\geq 3$  symptom attributable to intracranial or brain edema, the AE will be considered a DLT and the subject must permanently discontinue study treatment.

Note: Any AE of grade 3 or greater that is suspected to be attributable to brain edema will be considered an AESI and must be reported to the study sponsor (overall PI) within 24 hours of awareness of the event per **Section 8.3.1**. The study sponsor or designee will then notify the NYU DSMC and IRB within 24 hours of awareness of the event.

Note: Immune cell infiltration may be associated with increasing enhancement and edema on brain MRI or CT (i.e. pseudoprogression) and may mimic therapy-related central nervous system radiation necrosis or disease progression. Due to the well-described difficulty in differentiating between immune-mediated pseudoprogression and true tumor progression using standard imaging techniques, particularly in brain tumors, special attention must be made to events that are suspected to be attributed to possible brain edema and central nervous system necrosis.

For guidelines on managing radiographic findings, refer to **Section 6.7, Efficacy Procedures** and **Attachment 3, iRANO** criteria. A symptom or AE is initially suspected to be due to pseudoprogression or central nervous system necrosis may be later considered to be due to **disease progression** after review of additional imaging, biopsies and consultations with the treating investigators by the Safety Monitoring Team. These events may be reviewed for dosing decisions during the Safety Lead-In and toxicity monitoring during the phase II trial.

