**No Avelumab dose reductions are permitted.**

If Avelumab is temporarily withheld, the cycle count should be interrupted. Subjects who experience an adverse event that requires a treatment delay should be monitored with appropriate laboratory testing or other clinical evaluation at least weekly until resolution.

If Avelumab is discontinued (either permanently or temporarily) for an AE, the subject will generally discontinue the combination therapy treatment (HFRT) as well. If, however, a subject experiences an AE that in the opinion of the investigator is SOLELY related to HFRT, Avelumab may be continued and HFRT may be discontinued as per **Section 5.2.3.4**. Conversely, if a subject experiences an AE that in the opinion of the investigator is SOLELY related to Avelumab, then HFRT may be continued while Avelumab may be discontinued as per **Section 5.2.3.2**.

CONFIDENTIAL

**Table 2: Guidelines for Avelumab Hold and/or Discontinuations for Symptoms Related to Brain Edema or Central Nervous System Necrosis**

Grade	Hold Avelumab?	Restarting Criteria	Discontinuation Criteria
1	No	N/A	N/A
2	Consider withholding for persistent symptoms Consider bevacizumab if symptoms persist 	Toxicity resolves to Grade 0–1 or baseline	Toxicity does not resolve to Grade 0–1 or baseline within 14 days of last infusion or requires >8 mg/day of dexamethasone or bioequivalent for >7 consecutive days to treat symptoms
3	Yes Initiate bevacizumab in addition to appropriate symptomatic treatment 	Toxicity resolves to Grade 0–1 or baseline	Toxicity does not resolve to Grade ≤2 within 7 days, or to Grade ≤1 or baseline within 14 days of last infusion, or requires >8 mg/day of dexamethasone or bioequivalent for >7 consecutive days to treat symptoms
4 	Yes	N/A	Patient must be discontinued

**Note:** Per CTCAE v4.03, the AE "**Edema cerebral**" only has Grade 4 severity. The AE "Edema cerebral" should be used only if the symptom severity meets the CTCAE v4.03 criteria (i.e., "Life-threatening consequences; urgent intervention indicated"). See **Rules for Brain Edema, Section 5.2.1.2**

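### Section 5.2.1.2 gives two incompatible DLT rules for a Grade 3 brain-edema event that does not resolve and does not reach Grade 4

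*Combined protocol and SAP*

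**What the plan says.** All of the following is in Section 5.2.1.2 unless stated otherwise.

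- **General definition.** A DLT is any adverse event of Grade 3 or higher "that is at least possibly, probably or definitely related to Avelumab or HFRT during the DLT period with the exceptions noted below".
- **Exception list.** Among the events not classed as DLTs are Grade 3 or lower "symptoms attributable to brain edema, per details in the" Rules for Brain Edema. The exception is therefore defined by those Rules.
- **Rules for Brain Edema, opening paragraph.** After noting that edema may be silent or may cause symptoms up to severe, it says brain edema is expected with HFRT and will not "be considered a DLT unless brain edema meets CTCAE 4.03 criteria for" Edema cerebral (Grade 4 only). Four criteria define that Grade 4 event: neurosurgery, an osmotic diuretic, dexamethasone above 8 mg/day for more than 7 consecutive days, or a judgement that it is life-threatening.
- **Rules for Brain Edema, later paragraph.** Grade 3 or lower events attributable to edema or CNS necrosis escape DLT status on conditions. A Grade 3 event must fall to Grade 2 or lower in 7 days, or to Grade 1 or lower (or baseline) "within 14 days after onset of the event with maximal supportive care, including bevacizumab (see bevacizumab guidelines below"), within a dexamethasone limit.
- **Stopping rule.** For a patient whose edema symptoms have not settled to baseline or Grade 1 "by 2 weeks after the last dose of Avelumab, the subject must permanently discontinue study treatment".
- **Adjudication.** The Safety Monitoring Team rules on each case, and its "final decision of whether or not the AE meets the DLT definition will be based on a careful review of all relevant data".
- **Dose decision (Section 5.2.1.1).** At Dose Level 0 (10 mg/kg), at most 1 DLT in the first 6 subjects leads to phase II at that dose. More than 1 leads to Dose Level -1 (3 mg/kg).

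**The concern.** The opening sentence of the Rules is unconditional: short of Grade 4 Edema cerebral, edema does not count. The later paragraph is conditional: short of Grade 4, edema symptoms do not count provided they resolve in time. For a Grade 3 event that fails to resolve, both cannot be followed.

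This is the toxicity that the lead-in most needs to capture. Section 1.5.3 names potentiated radiation necrosis and severe neurotoxicity as the overlapping risk of the two treatments and gives that as the reason for the lead-in. Taken at its word, the opening sentence would leave an unresolved Grade 3 neurological event out of the count that sets the phase II dose.

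**Working it through.** The plan gives no figure on this point. The check compares the rules and then follows one classification through the dose decision.

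**Step 1: isolate the disputed event.** Take a related Grade 3 event attributable to brain edema, with onset in the DLT period and none of the four Grade 4 criteria met.

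| Course of the event | Opening sentence | General definition with conditional exemption |
|---|---|---|
| Resolves within the 7- or 14-day limit | Not a DLT | Not a DLT |
| Does not resolve in time, no Grade 4 criterion met | Not a DLT | DLT |
| Meets a Grade 4 criterion | DLT | DLT |

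Only the middle row conflicts. The dexamethasone limit adds little to it, because exceeding 8 mg/day for more than 7 consecutive days to manage edema symptoms is itself a Grade 4 criterion. The disputed events are essentially those that fail on time alone. The opening sentence names edema only, while the later paragraph names edema and CNS necrosis. The clash is therefore most direct for edema, and extends to necrosis that presents with edema.

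**Step 2: does the stopping rule settle it?** For suspected treatment-related "symptomatic intracranial or brain edema at any time during the study, Avelumab dosing should be" interrupted at once, so the last infusion is no later than onset. The stopping deadline (last infusion + 14 days) is then no later than onset + 14 days. An event still above Grade 1 and above baseline 14 days after onset has missed that deadline, so the patient stops Avelumab under either DLT rule. The stopping rule protects the patient but says nothing about the count.

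**Step 3: follow the classification through Section 5.2.1.1.** Let k be the number of DLTs among the other 5 subjects at Dose Level 0, with one disputed event in the sixth.

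| k | Count under opening sentence | Count under conditional rule | Decision |
|---|---|---|---|
| 0 | 0 | 0 + 1 = 1 | Dose Level 0 under both |
| 1 | 1 | 1 + 1 = 2 | Dose Level 0 versus de-escalation |
| 2 or more | at least 2 | at least 3 | De-escalation under both |

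One disputed event changes the dose only when k = 1. The same cut (at most 1 versus more than 1) applies at the lower levels. At Dose Level -2, more than 1 DLT ends the lead-in and phase II is not conducted.

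**The case against.** **The detail governs.** A general opening statement followed by specific conditions is normally read with the conditions controlling. On this view the opening sentence concerns the CTCAE term Edema cerebral, and the later paragraph concerns the symptoms. The exception list points to the Rules for their details, which supports this. It is the natural reading and I accept it as the likely intent. It does not remove the conflict: the sentence before the opening rule expressly covers edema with severe symptoms, the rule has no resolution condition, and nothing says which paragraph prevails.

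**The Safety Monitoring Team decides.** True, but that settles who classifies the event and leaves open which rule they apply.

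**Stronger readings that a reader might infer, and why they fail.**

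- *That timing the mandatory stop from the last infusion is an error.* Recovery time is 14 - d days for onset d days after an infusion, against 14 days from onset in the DLT exemption. But the text and Table 2 agree with each other, and with 14-day dosing the rule can be read as fit for the next scheduled dose. A stopping rule answers a different question from a DLT rule and may be stricter. An onset clock would let the decision run to 13 + 14 = 27 days after the last infusion, which is a clinical trade-off.
- *That Table 2 sets a looser Grade 3 threshold than the text.* Its trigger reads "Toxicity does not resolve to Grade ≤2 within 7 days, or to Grade ≤1 or baseline within 14 days of last infusion", and the word 'or' is ambiguous. The restart column requires Grade 0-1 or baseline on either reading, so nobody resumes at Grade 2.
- *That a de-escalation probability or a loss of power for PFS6 can be stated.* Section 7.1.3 does score patients off treatment before 6 cycles as failures, but the documents give no rate or duration for these events. Any such figure would rest on invented inputs.

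**Conclusion.** The conflict is real and narrow. It concerns a related Grade 3 event attributable to brain edema (or to CNS necrosis with edema) that does not resolve in time and meets no Grade 4 criterion. The opening sentence says it is not a DLT; the general definition with the conditional exemption says it is. The conditional rule is probably intended.

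The consequence is one unit in the lead-in count, which is decisive when exactly one of the other five subjects at that dose has a DLT. This rests only on the text of Sections 5.2.1.1 and 5.2.1.2. How often it would arise is unknown. The correction is worth making because it costs almost nothing and the event concerned is the one the lead-in was designed to watch. No error is claimed in the stopping clock.

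**What to change.** Amend the opening sentence of the Rules for Brain Edema to say that brain edema is not a DLT unless it meets Grade 4 Edema cerebral, or unless an attributable adverse event of Grade 3 or lower fails the resolution conditions set out later in the Rules.

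That paragraph also sets a condition for Grade 2 events, although the general definition starts at Grade 3. If only Grade 3 events are meant to count, the clause should say so.

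Two clarifications are optional: state the rationale for timing the mandatory stop from the last infusion, and align the Grade 3 wording in Table 2 with the text of Section 5.2.1.2.

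The cost is one clause of protocol text. Sample size, visits, assessments and the stopping rule do not change.
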